8.2.7 Dose Limiting Toxicity (DLT)

The number and percentage of subjects experiencing a DLT will be summarized and presented by dose level. A listing of DLTs will also be presented.

8.3 Clinical Laboratory Assessments

Laboratory assessments will be summarized by presenting descriptive statistics of raw data and change from baseline. Listings will include flags for values outside of the reference ranges, and clinical significance if a laboratory result is deemed abnormal.

The following tests will be performed by the central laboratory:

- Hematology
- Chemistry (with eGFR)
- HbA1c
- Coagulation (aPTT and either INR or PT)
- Thyroid function (TSH and FT4)
- Serum cytokines
- Histamine
- Complement
- Immunoglobulins
- B-cell count and immunophenotype (flow cytometry)

The following laboratory tests will be performed in the local laboratory at the site:

- Urinalysis (Dipstix)
- Pregnancy test (serum or urine)
- Serology for HIV, HBV and HCV (if applicable)

A shift table displaying baseline CTCAE grade to maximum post-baseline CTCAE grade will be presented for hematology and chemistry lab values.

8.4 Physical Examination

The overall results of the physical examination ('normal', 'abnormal, not clinically significant', or 'abnormal, clinically significant') and ECOG performance status will be summarized by treatment group / cohort and listed per subject. Comments for abnormal CS results will be listed.

8.5 Vital Signs

Vital sign data including weight, systolic blood pressure, diastolic blood pressure, heart rate, and temperature, will be summarized by presenting descriptive statistics of raw data and change from baseline values at each visit.

A shift table displaying baseline to maximum post-baseline values and last post-baseline value will be presented.

8.6 ECG Results

The following ECG results will be summarized.

- Heart rate
- PR interval
- QRS duration
- RR interval
- QT interval
- QT interval corrected according to Fridericia's formula (QTcF)

The results of the overall ECG review by the investigator or delegate will also be summarized. Comments for abnormal CS results of the ECG will be listed.

QTcF values will also be categorized according to their values as defined in ICH E14:

- ≤ 450 ms
- > 450 ms to ≤ 480 ms
- > 480 ms to ≤ 500 ms
- > 500 ms

and categorized according to their change from baseline into the categories

- ≤ 30 ms
- > 30 ms to ≤ 60 ms
- > 60 ms

The categories described above will be summarized in frequency tables using number of patients (n) and percentages for each dose cohort.

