6.2.3 Physical examination (PE)

A PE will be performed by a physician or a qualified delegate at the investigating site.

The full PE will be performed at the following time points:

- At screening
- At the EoT Visit

Abbreviated PE:

- Before MT-3724 dose on D1 of each cycle

The investigator or delegate at the site will perform the PE and evaluate the results. The PE can be captured up to 24 hours before dosing and must be done before dosing is allowed. The overall PE result will be categorized as 'normal', 'abnormal, not clinically significant (NCS)', or 'abnormal, clinically significant (CS)'. Any abnormal CS result of the PE should be followed up at the investigator's discretion and reported as an AE in the electronic CRF

(eCRF). Comments about abnormal NCS result of the PE, either overall or for individual aspects or body parts, will not be collected in the eCRF.

Complete physical examination

At a minimum, the following aspects/body parts should be assessed during the complete PE:

- General appearance
- Skin (paleness, jaundice, redness/rash, acneiform changes)
- Extremities (petechial bleedings, ulcers, signs of thrombosis), hands and feet (signs of hand-foot syndrome/palmar-plantar erythrodysesthesia)
- Ears, eyes (jaundice, inflammation), nose and throat (presence of petechial bleedings, gingival bleeding)
- Head and neck
- Lungs
- Heart
- Abdomen (pain, tenderness, peristaltic, ascites, organomegaly)
- Lymph nodes
- Neurological examination to include the following assessments:
 - Oculomotor testing, pupil accommodation, double images
 - Motor system: muscle strength of arms
 - Sensory system: pain and touch sensation of thighs
 - Mental Status
 - Posture
 - Coordination: finger-to-nose and heel-to-shin test
 - Reflexes: biceps, patella and plantar (Babinski's sign) test
 - Gait: walking freely, on toes and on heels
 - Romberg test

Other aspects/body parts or organ systems may be assessed at the investigator's discretion.

Abbreviated physical examination

At a minimum, the following aspects/body parts should be assessed during the abbreviated PE:

- General appearance
- Skin (paleness, jaundice, redness/rash, acneiform changes)
- Ears, eyes (jaundice, inflammation) nose, throat (presence of petechial bleedings, gingival bleeding)
- Lungs
- Heart
- Abdomen (pain, tenderness, peristaltic, ascites, organomegaly)

- Lymph nodes

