6.2.8 Electrocardiograms

Standard resting 12-lead ECG assessments will be performed after the subject had rested rest quietly for 5-10 minutes in supine or semi-recumbent position. The ECG recordings will be obtained at the following time points:

- At screening (triplicate ECG, i.e. 3 ECG recordings obtained in close succession and not more than 2 minutes apart)
- Before the start of MT-3724 infusion on D1 of each cycle (single ECG recording will be performed)
- At the EoT Visit (single ECG)

If the ECG printout is of poor quality, additional ECG(s) may be obtained at the same time point until an ECG of adequate quality is obtained. Such additional ECG(s) do not have to be reported as unscheduled assessments.

When PK, ECG and VS assessments are scheduled to occur at the same time point, the ECG and VS should be done first and in that order, with the timing of assessments based on collecting the PK sample at the protocolled time.

The investigator or delegate at the site will assess the ECG results. The three QTcF values from a triplicate ECG should be averaged to yield the QTcF value for the purpose of eligibility assessment. The derived variable will be calculated according to the formula of Fridericia using an online calculator.

The overall ECG assessment will be categorized as ‘normal’, ‘abnormal, not clinically significant (NCS)’, or ‘abnormal, clinically significant (CS)’. The overall ECG assessment by the ECG recorder and the related diagnostic comments will not be entered in the eCRF.

Any clinically significant abnormality in the ECG should be investigated by unscheduled ECG assessment(s) (number and timing at investigator's discretion). The confirmed clinically significant abnormalities should be reported as AE in the eCRF.

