7.2 General statistical considerations

Statistical analysis will be performed using the Statistical Analysis System®; the version used will be specified in the statistical analysis plan (SAP).

All data will be listed, and descriptive summary tables will be provided by treatment group/cohort irrespective of the study part. In addition, appropriate variables will be summarized in a separate treatment group comprising the subjects treated at the MTD of MT-3724 in Part 1 (dose escalation) and in Part 2 (expansion). These variables will be specified in the SAP.

Quantitative data will be described by the following summary statistics: arithmetic mean, standard deviation, median, minimum, and maximum. Where appropriate, descriptive summary statistics will be tabulated for the absolute values and changes from baseline. Graphical illustrations will be provided where appropriate. Qualitative data will be presented in the frequency tables.

The assessment obtained at the most recent time before the start of MT-3724 treatment will be the baseline for all post-baseline assessments. The value obtained before MT-3724 Dose 1 on C1D1 (if available) will serve as the baseline; if not available, then the value obtained earlier at screening will serve as the baseline.

Further details about the statistical analyses will be provided in the SAP. Any changes in the statistical methods described herein compared to the final SAP will be documented in the integrated clinical study report.

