5.3 Assessment Windows

Data will be summarized based on the CRF (Study Visit) in which it was collected even if the assessment is outside of the specified visit window. In data listings, the relative day of all dates will be presented. Such days will be measured relative to Day 1, the day in which the first dose of study drug is received.

The last post-baseline visit where data were collected will be flagged for each subject. These visits will be combined for analysis of laboratory and vital sign results.

The assessment obtained at the most recent time before the start of MT-3724 treatment will be the baseline for all post-baseline assessments. The value obtained before MT-3724 Dose 1 on C1D1 (if available) will serve as the baseline; if not available, then the value obtained earlier at screening

will serve as the baseline. Screening procedures should be performed up to 28 days before Day 1 C1D1.

If a repeat laboratory sample was drawn for a visit, the values from the repeat sample will be used for summary and analysis purposes. In this case, only the repeat sample values will be listed.

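### When a C1D1 ECG exists, SAP 8.6 measures QTcF change from one single recording; averaging in the screening triplicate would cut chance results above 30 ms

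*SAP*

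**What the plan says.** The general baseline rule is in SAP 5.3: "The value obtained before MT-3724 Dose 1 on C1D1 (if available) will serve as the baseline". A second clause covers subjects without a C1D1 reading: "if not available, then the value obtained earlier at screening". Protocol 7.2 has the same rule with the same screening fallback: "The value obtained before MT-3724 Dose 1 on C1D1 (if available) will serve as the baseline; if not available".

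Protocol 6.2.8 sets the number of recordings. Screening has a triplicate, taken within minutes. On treatment the entry is "Before the start of MT-3724 infusion on D1 of each cycle (single ECG recording will be performed", which includes C1D1, and the EoT ECG is also single. The three screening QTcF values are "averaged to yield the QTcF value for the purpose of eligibility assessment", with exclusion above 480 ms (protocol 4.2, criterion 8).

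SAP 8.6 places QTcF into absolute classes "and categorized according to their change from baseline into the categories" at cut-points of 30 and 60 ms, by dose cohort. It gives no ECG-specific baseline. It does not say whether the triplicate average or one of its readings is used when screening is the fallback. Nor does it say whether a subject is classified by the worst later value or visit by visit.

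**The concern.** On schedule, every QTcF change is one single ECG minus another. A C1D1 reading that is low by chance raises all later changes for that subject, so counts above 30 ms partly reflect baseline noise. Three more drug-free recordings exist from screening and are not used for this purpose. If C1D1 is missing, the baseline may be of a different type, so its precision can differ between subjects.

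ECG results belong to the primary safety analysis (protocol 7.8). Cohorts start at 3 or 4 subjects and may expand to 6 (protocol 3.6), so one false outlier is 17 to 33% of a cohort's row.

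**Working it through.** **Inputs from the documents.** One ECG at C1D1, at D1 of each later cycle and at EoT; three ECGs at screening; cut-points of 30 and 60 ms; up to 40 subjects in Part 2. There is no QTcF SD and no expected outlier rate, so no figure of the plan's own to reproduce.

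**Assumptions.** No drug effect; normal errors; occasions independent; occasion SD *so* and recording SD *sr* as in the table; a subject counted by the worst of four post-baseline ECGs.

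**Variances.**
- Single ECG (C1D1 or later): so² + sr².
- Screening triplicate mean: so² + sr²/3.
- Mean of the triplicate mean and C1D1: [(so² + sr²/3) + (so² + sr²)]/4 = so²/2 + sr²/3.

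**Hand check for one later ECG, (so, sr) = (8, 6).**
- Single baseline: change variance 100 + 100 = 200, SD 14.14 ms; P(change > 30) = 1 − Φ(30/14.14) = 1.7%.
- Averaged baseline: 32 + 12 = 44; change variance 144, SD 12 ms; P = 1 − Φ(2.5) = 0.6%.

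**Worst of four later ECGs** (simulation, 1,000,000 subjects), percentage above 30 ms:

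| so, sr | Single C1D1 | Triplicate mean alone | Two single ECGs, two days | Triplicate mean averaged with C1D1 | Ratio, single to averaged |
|---|---|---|---|---|---|
| 6, 6 | 2.2 | 1.2 | 0.7 | 0.6 | 3.7 |
| 8, 6 | 5.5 | 4.1 | 2.7 | 2.4 | 2.3 |
| 10, 8 | 14.1 | 11.8 | 9.5 | 8.8 | 1.6 |
| 12, 8 | 19.4 | 17.6 | 14.6 | 13.9 | 1.4 |

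The triplicate mean alone improves on the single baseline only 1.1 to 1.9 times. Two single ECGs on two days give nearly the full gain, so the benefit comes mainly from the second occasion.

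**Counts at (8, 6).** In 40 subjects: 40 × 5.5% = 2.2 against 40 × 2.35% = 0.9. In a cohort of 3 to 6: 0.16 to 0.33 against 0.07 to 0.14 expected subjects.

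**Above 60 ms.** Single baseline: 0.005% at (8, 6) and 0.6% at (12, 8). Averaged baseline: below 0.001% and 0.1%.

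**Wider assumptions.** Let the total SD of one ECG run from 8 to 20 ms, and the share of its variance common to the three replicates from 0 to 0.9. The averaged baseline then gives ratios of about 1.1 to 6.3 for the worst of four ECGs. The triplicate mean alone gives 1.03 to 6.9 for one later ECG. The largest ratios belong to very small rates (at SD 8 with independent replicates, 0.40% against 0.06%).

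**Shift between screening and C1D1.** If screening QTcF is systematically lower by d, the averaged baseline is too low by d/2. Percentage above 30 ms, averaged baseline:

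| so, sr | d = 6 | d = 8 | d = 10 | Single C1D1 |
|---|---|---|---|---|
| 6, 6 | 1.4 | 1.9 | 2.5 | 2.2 |
| 8, 6 | 4.5 | 5.4 | 6.6 | 5.5 |
| 10, 8 | 13.1 | 14.9 | 16.7 | 14.1 |
| 12, 8 | 19.0 | 21.0 | 23.0 | 19.4 |

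Break-even lies between 6 and 10 ms in all four cases. By 10 ms the gain has gone.

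**The case against.** **The C1D1 baseline is a defensible choice.** It is closest to treatment and matches the later pre-dose Day 1 ECGs in timing and type. Screening may be up to 35 days earlier (protocol 3.2; SAP 5.3 still says 28), and its average is truncated at 480 ms by eligibility. A drift would bias an averaged baseline: upward drift adds false outliers, downward drift hides real increases. This stands, and is why the C1D1-only change should also be shown.

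**Little hangs on the table.** SAP 8 plans no hypothesis test between dose levels, and protocol Appendix 4 names no QTcF-change threshold. Absolute QTcF classes, which need no baseline, are tabulated beside it. Clinically significant ECG abnormalities are followed by repeat ECGs and, if confirmed, reported as AEs. All of this stands and limits the weight of the point.

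**Stronger readings that a reader might infer, and that the documents do not support:**
- That C1D1 is always the baseline and the triplicate is never used. The rule applies only if a C1D1 value is available, screening is the fallback, and the triplicate average decides eligibility.
- That a fixed inflation factor follows from the plan, or from ignoring the triplicate as such. The SDs are assumed, and the triplicate mean alone gains much less than a second occasion.
- That the same rule spoils the physical examination summary, because C1D1 has the abbreviated exam while the full one is at screening and EoT (protocol 6.2.3, "The full PE will be performed at the following time points"). SAP 8.4 says that "The overall results of the physical examination" are summarised and listed, and plans no comparison with baseline. Shift tables are specified for laboratory values and vital signs only. Protocol 7.8 mentions changes in examination but defines no comparison.

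**Conclusion.** The point holds for ECG intervals only. With a C1D1 ECG on file, as the schedule requires, QTcF change rests on a single baseline recording, and the screening triplicate does not enter it. Under the assumptions stated, chance alone puts about 2 to 19% of subjects above 30 ms, against about 0.6 to 14% with the two-occasion baseline: a ratio of about 1.4 to 3.7, wider under other SDs. These sizes need no drift between screening and C1D1, and classification by the worst of four ECGs, which SAP 8.6 does not specify. The absolute effect in a small cohort is a fraction of a subject, and the class above 60 ms is almost unaffected. This is an inexpensive improvement to a descriptive safety table. It does not threaten any dose decision or conclusion of the trial.

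**What to change.** In SAP 8.6, as a stated exception to SAP 5.3, define the baseline for QTcF and the other ECG intervals as the mean of two values: the average of the screening triplicate and the C1D1 pre-dose value. State that the triplicate average serves alone if the C1D1 ECG is missing. List the change from C1D1 alone beside it, so that a shift between screening and C1D1 can be seen. Make the change before database lock, so that the baseline is not chosen after the outliers are known.

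The cost is two or three sentences, one extra listing column, and an ECG baseline that differs from the general rule. No new recordings and no change to study conduct are needed. SAP 8.4 needs no change on this account.

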9. INTERIM ANALYSIS

No interim statistical analysis is planned during either part of this study. An interim statistical analysis may be performed only pursuant to a health authority request.

Informal (preliminary) statistical analyses may be performed at sponsor's discretion at any time during the study. These analyses would be performed without the interim data base lock for the purposes of the IB update, safety reports to the health authorities (e.g. DSUR), and meetings with health authorities or for internal decisions.

In addition, data from individual subjects and cohorts will be reviewed without formal statistical analysis on an ongoing basis during the study (e.g. to support the dose escalation decisions in Part 1).

10. SAMPLE SIZE AND POWER CALCULATIONS

Up to 64 subjects (i.e., up to 24 subjects in Part 1 and up to 40 subjects in Part 2), as well as the appropriate number of replacements (if needed), will be enrolled and treated in this study. The actual number will depend on the number of dose cohorts needed to identify the MTD of MT-3724 in combination with LEN in Part 1.

This is an exploratory Phase 2a study, so the formal power calculation is not deemed necessary to justify the sample size. The proposed sample size is deemed sufficient for the adequate characterization of the study objectives and would be typical of the sample sizes of exploratory Phase 1b / 2a studies with novel anti-cancer agents

12. APPENDICES

12.1 Appendix A: Schedule of Assessments

Insert schedule of assessments from protocol.

12.2 Appendix B: Example HLA Mismatch Calculations

HLA: Mismatched Antigens

D O N O R	RECIPIENT						
		A01	A02	B07	B08	DR13	DR15
	A01	Green					
	A02		Green				
	B07			Green			
	B08				Green		
	DR13					Green	

0 Antigen Mismatch

D O N O R	RECIPIENT						
		A01	A02	B07	B08	DR13	DR15
	A01	Green					
	A03		Red				
	B07			Green			
	B08				Green		
	DR13					Green	

1 Antigen Mismatch

D O N O R	RECIPIENT						
		A01	A02	B07	B08	DR13	DR09
	A01	Green					
	A02		Green				
	B44			Red			
	B08				Green		
	DR13					Green	

Antigen Mismatch

2

D O N O R	RECIPIENT						
		A01	A11	B07	B22	DR08	DR15
	A01	Green					
	A02		Red				
	B07			Green			
	B08				Red		
	DR13					Red	

3 Antigen Mismatch

D O N O R	RECIPIENT						
		A01	A02	B07	B08	DR13	DR15
	A03	Red					
	A02		Green				
	B60			Red			
	B51				Red		
	DR13					Green	

4 Antigen Mismatch

D O N O R	RECIPIENT						
		A01	A02	B27	B08	DR11	DR15
	A24	Red					
	A33		Red				
	B07			Red			
	B08				Green		
	DR13					Red	

5 Antigen Mismatch

D O N O R	RECIPIENT						
		A01	A02	B07	B08	DR13	DR15
	A24	Red					
	A33		Red				
	B27			Red			
	B56				Red		
	DR17					Red	

6 Antigen Mismatch

MATCH

MISMATCH

Homozygosity: Instances in which antigens are not defined are typically a result of homozygosity. Homozygosity is defined as the condition of having identical genes at one or more loci (A, B, DR). As HLA genes are inherited from the mother and the father, if the mother and father share an antigen or multiple antigens, it is possible for a child to inherit the same A and/or B and/or DR antigen from both parents. When this occurs, antigens suspected to be duplicated are termed “blank”, and the results will appear as shown below.

		RECIPIENT					
		A01		B03		DR13	
D O N O R	A01	Green					
			Yellow				
	B03			Green			
				Yellow			
	DR13				Green		
						Yellow	

Example 1

0 Antigen Mismatch

(“blanks” on donor and recipient)

No antigens differ between the recipient and donor. This combination would qualify as a 0 antigen mismatch.

		RECIPIENT					
		A01	A02	B03	B44	DR13	DR17
D O N O R	A01	Green					
	B03			Green			
	DR13				Green		

Example 2

0 Antigen Mismatch

(“blanks” on donor only)

Because the donor does not express any antigens the recipient does not express, this combination would also qualify as a 0 antigen mismatch.

		RECIPIENT					
		A01		B03		DR13	
D O N O R	A01	Green					
	A02		Red				
	B03			Green			
	B44				Red		
	DR13					Green	
	DR17						Red

Example 3

3 Antigen Mismatch

(“blanks” on recipient only)

If Example 2 is reversed and the donor expresses antigens that the recipient does not, these will qualify as mismatched antigens. The recipient immune system *may now recognize the A02, B44, and DR 17 from the donor as foreign and mount an immune response.*

MATCH

MISMATCH

**SUSPECTED
MATCH**
